### 13.0 BIOHAZARD CONTAINMENT

As the transmission of HIV and other blood-borne pathogens can occur through contact with contaminated needles, blood, and blood products, appropriate blood and secretion precautions will be employed by all personnel in the drawing of blood and shipping and handling of all specimens for this study, as currently recommended by the CDC and the National Institutes of Health.

All dangerous goods and materials, including diagnostic specimens and infectious substances, must be transported using packaging mandated by CFR 42 Part 72. Please refer to instructions detailed in the International Air Transport Association (IATA) Dangerous Goods Regulations.

## PROTOCOL SUMMARY

### PREP AND DPEP: DOXYCYCLINE POST-EXPOSURE PROPHYLAXIS FOR PREVENTION OF SEXUALLY TRANSMITTED INFECTIONS AMONG KENYAN WOMEN USING HIV PRE-EXPOSURE PROPHYLAXIS

**Design:** Open-label 1:1 randomized clinical trial of doxycycline PEP (dPEP) to reduce bacterial STIs – *Neisseria gonorrhoeae*, *Chlamydia trachomatis*, and *Treponema pallidum* (syphilis) – among Kenyan women taking PrEP. We will also use quantitative questionnaires, focus group discussions, SMS, and in-depth interviews to study acceptability, adherence, and changes in sexual behavior due to dPEP.

**Study Population:** 446 Kenyan women aged  $\geq 18$  and  $\leq 30$  years old taking PrEP randomized to dPEP and standard of care vs. standard of care alone

**Study Sites:** KEMRI RCTP – Lumumba clinic

**Primary Study Objectives:**

1. Evaluate the effectiveness of doxycycline post-exposure prophylaxis (dPEP) to reduce STI infections in HIV-uninfected Kenyan women taking HIV PrEP
2. Assess the safety, tolerability, and acceptability of dPEP
3. Assess adherence to dPEP
4. Investigate the impact of dPEP on tetracycline resistance in *N. gonorrhoeae* and *C. trachomatis*
5. Measure the cost of dPEP and estimate the cost per case averted, budget impact, and affordability.

## LIST OF ABBREVIATIONS

Table 1: List of Abbreviations

AE	Adverse event
AMR	antimicrobial resistance
ART	Antiretroviral therapy
CDC	Centers for Disease Control
CT	Chlamydia trachomatis
DAIDS	Division of AIDS
DALY	Disability-adjusted life year
dPEP	Doxycycline post-exposure prophylaxis
DSMB	Data safety and monitoring board
FGD	Focus group discussion
GEE	Generalized estimating equations
HAL	Hair Analytical Laboratory
HIV	Human Immunodeficiency virus
HSV	Herpes simplex virus
IATA	International Air Transport Association
ICER	Incremental cost effectiveness ratio
IDI	In-depth interviews
IH	Intracranial hypertension
IRB	Institutional Review Board
IPV	Intimate partner violence
KEMRI	Kenya Medical Research Institute
LARC	Long-acting reversible contraceptives
LMP	Last menstrual period
MOH	Ministry of Health
MSM	Men who have sex with men
NAAT	Nucleic acid amplification test
NASCOP	National AIDS & STI Control Programme
GC	Neisseria gonorrhoeae
PCR	Polymerase chain reaction
PEP	Post-exposure prophylaxis
PID	Pelvic inflammatory disease
PLWH	People living with HIV
RPR	Rapid Plasma Reagins
SAE	Serious Adverse Event
SMS	Short message service

STIs	Sexually transmitted infections
TDF/FTC	Tenofovir/Emtricitabine
tetR	Tetracycline resistant
UCSF	University of California San Francisco
UW	University of Washington
VCT	Voluntary counseling and testing

## **1. INTRODUCTION**

The purpose of this document is to provide details on study populations and on how the variables will be derived, how missing data will be handled as well as details on statistical methods to be used to analyze the safety and efficacy data. This SAP only details the analysis of primary and key secondary objectives.

The document may evolve over time, for example, to reflect the requirements of protocol amendments or regulatory requests. However, the final SAP will be finalized, approved by the Protocol Chairs, and placed on file before database is locked.

## 2. STUDY OBJECTIVES AND ENDPOINTS

### 2.1. Study Objectives

#### 2.1.1. Primary Efficacy and Safety Objectives

1. Evaluate the effectiveness of doxycycline post-exposure prophylaxis (PEP) to reduce STI infections in HIV-uninfected Kenyan women taking HIV PrEP
2. Assess the safety, tolerability, and acceptability of dPEP

#### 2.1.2. Secondary objectives

1. Assess adherence to dPEP
2. Investigate the impact of dPEP on tetracycline resistance in *N. gonorrhoeae* and *C. trachomatis*
3. Measure the cost of dPEP and estimate the cost per case averted, budget impact, and affordability

### 2.2. Study Endpoints

#### 2.2.1. Primary Efficacy Endpoints

##### Effectiveness of doxycycline

The primary endpoint is assessed using the following STI endpoints at month 3, 6, 9 and 12 visits:

- Documented positive vaginal/cervical GC
- Documented positive vaginal/cervical CT
- Early syphilis infection based on four-fold increase in non-treponemal titers.

The primary trial endpoint is any newly diagnosed STI, defined as any one of the above after the enrollment visit, with the exception of re-diagnosis of the same infection at a test of cure visit within 28 days of first treatment of a baseline or incident infections (which is considered a non-cured infection and re-treated). Any infection newly diagnosed at an interim visit will be counted as a primary endpoint for the subsequent scheduled visit i.e., if a participant is diagnosed with new GC infection at an interim visit 40 days after their 6 month visit, this will be analysed as a primary 9 month endpoint. Endpoints are reviewed by committee, blinded to study arm, and primary endpoints designated in that review.

#### 2.2.2. Secondary Efficacy Endpoints

##### Efficacy of doxycycline for individual STIs

Effectiveness of doxycycline will also be assessed for CT and GC separately, using an incident STI definition that parallels the above for the specific infection.

### **2.2.3. Safety, tolerability and acceptability of dPEP**

- Safety:
  - serious adverse events (SAEs),
  - all related AEs (assessed in the dPEP arm only)
- Tolerability:
  - dPEP discontinuation (assessed in the dPEP arm only)
  - Candida yeast infection treatment (documented as fluconazole on STI treatment CRF)
  - Doxycycline-specific side effects (assessed via standardized symptom assessment: includes reports of nausea, pill esophagitis, photosensitivity)
- Acceptability:
  - Acceptability and Optimism questionnaire (FDAO) (13 question on a 5-point Likert scale)

### **2.2.4. Adherence**

Adherence is only assessed in the dPEP arm

- Weekly SMS questions
  - Weekly questions collected in participants who opted in to SMS.
  - Number of days in the last 7 days when dPEP was taken
  - Number of days in the last 7 days when participants had sex or “danced”).
- Hair samples
  - Collected quarterly
    - Quantitative amount of doxycycline in 1cm segments from cut end to tip which corresponds with a 4-week period of dPEP use (starting 1 week ago).
- Self-report of coverage of sexual contacts in the prior 14 days to 3 days in the dPEP arm:
  - Quarterly (timeline follow-back) adherence questionnaire.

### **2.2.5. Tetracycline resistance**

- Molecular markers of resistance for CT after enrollment (positive CT swabs collected at Enrollment, Month 3, 6, 9 and 12, as well as any test of cure visits)
- Molecular markers of resistance for GC after enrollment (positive GC swabs collected at Enrollment, Month 3, 6, 9 and 12, as well as any test of cure visits)

### **3. STUDY DESIGN**

#### **3.1. Summary of Study Design**

Open label 1:1 randomized trial of dPEP versus standard of care. Participants assigned to dPEP will be instructed to take doxycycline 200 mg (two 100mg capsules) orally within 24 hours and up to 72 hours after each condomless sex act as frequently as daily if indicated but not more than once daily.

At Months 0/3/6/9, women randomized to dPEP will receive doxycycline, sufficient for nearly daily use for 3 months (i.e., 100 capsules). Unused capsules will be counted at each follow-up visit (Months 3/6/9/12) and additional doxycycline will be given to total up to 180 capsules if needed. The medication, doxycycline hydiate, will be purchased from a quality-controlled supplier and with consultation by the Kenya National AIDS and STI Control Programme. Participants will also be offered single- or multi-dose pill carriers for ease of dosing dPEP following exposures. All participants will receive quarterly visits for standard of care prevention services and collection of clinical and behavioral data, for a total of 12 months of follow-up.

**Study visits:** Every 3 months, study visits will include STI screening, behavioral questionnaires, hair sample collection, and swab collection for archived samples. Women may return to the study clinic for interim visits for any reason and will undergo STI testing and treatment if STI symptoms are present. Participants with a new STI diagnosis will return for prompt treatment, provided on-site. Laboratory testing will be conducted by staff blinded to randomization assignment, and STIs will be reviewed by an Endpoint Adjudication Committee blinded to treatment arm. All participants diagnosed with an STI will either receive same day treatment or return to the research clinic for treatment, using WHO/Kenya standard therapies, avoiding doxycycline options, and a second visit two weeks following completion of STI treatment will be done for test of cure; this mitigates potential risk to participants and the community if resistance is selected.

**Study population:** This study will enroll approximately 446 Kenyan women aged 18 and 30 years old taking PrEP. PrEP use is an eligibility criterion for enrollment because we hypothesize that women engaging in PrEP are a priority population for prevention of curable STIs, given high incidence, interest in longitudinal preventative services, and willingness to take pills for prevention. Aligning with Kenya's national PrEP services, we propose an evaluation of the benefits, risks, and costs of dPEP among women, in the first trial of this intervention for this population. However, participants may opt to stop PrEP use at any time during the study without affecting their involvement in the study. Any HIV-uninfected participants who subsequently seroconvert will be managed clinically by the study site according to local practice (appropriate counseling, clinical evaluation and immediate linkage to clinical and psychosocial services). These participants will also be retained in the study unless they choose to discontinue study participation

### 3.2. Definition of Study Drugs

The study drug is open-label doxycycline 200 mg to be taken ideally within 24 hours but no later than 72 hours after condomless sexual contact (oral or anal). 200 mg of doxycycline will be taken at most once per 24 hour period regardless of the number of sexual acts occurring during this time period

### 3.3. Sample Size Considerations

#### 3.3.1. Sample Size Justifications

The study is a 1:1 randomized superiority design, comparing dPEP to standard of care. The primary trial outcome will be the combined incidence of incident *C. trachomatis*, *N. gonorrhoeae*, and syphilis infections, compared between the randomization arms, to mirror the IPERGAY and Doxy PEP approach; analyses will also test CT and NG alone. Sample size was determined using an event driven approach (N = 66). Assuming 10% loss-to-follow-up, incidence of 22% for any STI in the SOC arm and a two-sided alpha of 0.05, a sample size of n=446 (n=223 per arm) has 80% power to detect a 50% reduction in time to first STI, i.e. ~11% in the dPEP arm (n=44 vs. 22 cases).

The trial intends to have sufficient power to detect 50% effectiveness in CT alone, and thus not stop before incident diagnosis of CT has occurred in 66 women (resulting in more than the minimum number of composite events for the endpoint of any STI).

Sample sizes were computed using nQuery for time to first STI within one year of follow-up

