**Table 2 Power Table for N = 446; 1:1 randomization dPEP: SOC**

Control arm incidence	Power to detect 50% reduction (Number of infections for 80% power = 66)		Power to detect 65% reduction (Number of infections for 80% power = 52)	
	Intervention arm incidence	Power	Intervention arm incidence	Power
50%	25.0%	99%	17.5%	99%
33%	15.5%	93%	11.6%	99%
22%	11.0%	80%	7.7%	96%
18%	9.0%	71%	6.3%	92%
15%	7.5%	63%	5.2%	87%

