### **3.3.2. Sample Size Re-estimation**

At the point when enrollment is near completion, the study team will evaluate the expected power of the trial, based on the observed rate of infections. If the rate of the primary endpoint is substantially lower than anticipated, sample size re-estimation would be used to restore power to the extent possible, through additional enrollments, increase in person-time, or modification of risk criteria.

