## **4. PLANNED ANALYSES**

### **4.1. Interim Analyses**

The trial will be monitored by an independent data monitoring committee approximately every 6 months. The trial plans to continue until we have established definitive efficacy results, whether effective or ineffective, for both CT alone and for any STI. Two formal interim monitoring times are planned, when 1/3 and 2/3 of the follow-up visits have been completed, with stopping rules based on consideration of both the primary outcome and the CT outcome alone. Because the outcomes are highly correlated, no adjustment for multiple comparisons is planned. O'Brien-Fleming boundaries will be used, with stopping based on the alpha spending corresponding to observed p-values in the efficacy analyses. Stopping for both efficacy and lack of efficacy will be considered; however, a decision to stop for efficacy will need to balance the need for evidence assessing the potential harm of acquired tetracycline resistance.

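### SAP 3.3.1 plans on 22% incidence of any STI, which does not support its floor of 66 women with CT; no CT planning rate is given, and the re-estimation clause would not respond to a CT shortfall

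*SAP*

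**What the plan says.** - **SAP 3.3.1, composite.** The inputs are "Assuming 10% loss-to-follow-up, incidence of 22% for any STI in the SOC arm", a two-sided alpha of 0.05 and a 50% reduction in time to first STI. They lead to 66 events (44 vs 22) and 446 women, 223 per arm, for 80% power.
- **SAP 3.3.1, CT alone.** The trial is also meant to have enough power for a 50% effect on CT, and will "thus not stop before incident diagnosis of CT has occurred in 66 women". The section describes this as "resulting in more than the minimum number of composite events for the endpoint of any STI". It gives no CT incidence.
- **SAP Table 2**, headed "Power Table for N = 446; 1:1 randomization dPEP: SOC", lists power by control-arm incidence without naming the infection. For a 50% reduction it gives 80% at 22%, 71% at 18% and 63% at 15%. For a 65% reduction it gives 96%, 92% and 87%.
- **SAP 3.3.2.** Near the end of enrollment, "the study team will evaluate the expected power of the trial, based on the observed rate of infections". The action clause begins: "If the rate of the primary endpoint is substantially lower than anticipated". The levers listed are more enrollments, more person-time or changed risk criteria.
- **SAP 4.1.** "The trial plans to continue until we have established definitive efficacy results, whether effective or ineffective, for both CT alone and for any STI".
- **SAP 4.2** places the final analysis after the last 12-month visits and sets no CT condition.
- **Protocol summary** claims more than 80% power both overall and for CT alone, in a paragraph that gives both 550 women and 223 per arm.
- **Protocol section 10** plans on 22% STI incidence and calls this conservative because it is lower than the CT incidence in earlier cohorts (27%, 33% and 53% in Protocol Table 3). It also says the trial will continue until there are 66 CT events.

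**The concern.** Women with CT are a subset of women with any STI. A plan that expects about 66 women with any STI cannot also expect 66 with CT, unless almost nobody has gonorrhoea or syphilis alone. The SAP's own remark that the CT floor will produce more than the minimum number of composite events accepts that some women will have only a non-CT infection. The stated rate and the stated floor therefore do not fit together, and no CT rate is given that would reconcile them.

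The practical risk is a gap in the rules. If 22% really is the any-STI rate, the composite can run exactly to plan while CT falls short of 66. The re-estimation clause would then not be triggered, because the primary-endpoint rate is not low, and SAP 4.2 would proceed to final analysis at 12 months. The CT comparison would have less power than the Protocol summary claims, although SAP 4.1 undertakes to settle the question for CT as well as for the composite.

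**Working it through.** **Inputs** (SAP 3.3.1 unless noted): 223 per arm; 10% loss; any-STI risk 22% vs 11%; hazard ratio 0.5; two-sided alpha 0.05; 80% power. The Protocol section 10 alternative is 275 per arm.

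**1. Reproduce the plan.** Schoenfeld events = 4 × (1.960 + 0.842)² / (ln 0.5)² = 65.3, rounded up to 66. Then 66 / (0.22 + 0.11) = 200 per arm, and 200 / 0.9 = 222.2, so 223 per arm and 446 in total. This matches the SAP exactly.

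**2. Expected women with any STI.**
- N=446: 223 × 0.9 = 200.7 per arm; 200.7 × 0.22 + 200.7 × 0.11 = 44.2 + 22.1 = 66.2. Schoenfeld power is 80.5%.
- N=550: 275 × 0.9 = 247.5 per arm; 247.5 × 0.33 = 81.7.

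**3. CT share required if 22% is the any-STI rate** (50% effect on both).

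| | N=446 | N=550 |
|---|---|---|
| 66 women with CT | 66 / 66.2 = 99.7% | 66 / 81.7 = 81% |
| 80% first-event CT power (65.3 events) | 65.3 / 66.2 = 98.7% | 65.3 / 81.7 = 80% |

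**4. Illustration with two Table 2 rows.** The CT share is an assumption; neither document gives one. Expected CT women = evaluable per arm × CT rate × 1.5 for a 50% reduction.

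| Control-arm CT | Share of 22% | CT women, N=446 | Power, 50% reduction: Schoenfeld (Table 2) | Table 2 power, 65% reduction |
|---|---|---|---|---|
| 18% | 18/22 = 82% | 200.7 × 0.18 × 1.5 = 54.2 | 72% (71%) | 92% |
| 15% | 15/22 = 68% | 200.7 × 0.15 × 1.5 = 45.2 | 64% (63%) | 87% |

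At N=550 the same two rows give 66.8 and 55.7 CT women, with power of 81% and 73% for a 50% reduction.

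The 65% column is not inflated. Schoenfeld with 200.7 × 0.18 × 1.35 = 48.8 and 200.7 × 0.15 × 1.35 = 40.6 events gives about 96% and 92%.

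**5. The other reading of 22%.** If control-arm CT is itself 22%, N=446 gives 66.2 CT women and the expected shortfall is gone. At the Protocol Table 3 CT rates the expected numbers are 200.7 × 1.5 × 0.27 = 81, × 0.33 = 99 and × 0.53 = 160.

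**6. Which rule would respond to a CT shortfall?** The evaluation step in SAP 3.3.2 refers to infections in general, but its action step is conditional on the primary endpoint alone. SAP 4.2 depends on visits, not events. SAP 3.3.1 and Protocol section 10 state the floor but no check or action. A trial with 66 composite events and 54 CT events would leave the floor unmet, trigger no re-estimation and proceed to final analysis under 4.2.

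**The case against.** **The 22% is a deliberate minimum.** It lies below every CT rate the documents cite, and at those rates 81 to 160 women with CT would be expected at N=446. This stands. A reader might infer that the trial is expected to miss its CT floor, or is underpowered for CT. The documents do not support that. They support only that the stated inputs do not deliver the stated floor, and that the CT rate relied on is not written down.

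**The authors saw the subset relation and set a continuation rule.** Both documents commit to 66 CT events, SAP 4.1 bases stopping on CT as well as the primary outcome, and the Protocol's DSMB section includes the study's ability to meet its objectives. This also stands, and it shows intent. A reader might infer that the team must either exceed 446 women or finish below its floor. That goes too far, because SAP 3.3.2 also lists added person-time. What is missing is a condition linking those levers to CT.

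**The CT effect may exceed 50%.** Protocol section 10 anticipates this, and Table 2 then gives 92% and 87% at CT 18% and 15%. That is a fair answer on power, and any restatement should show both columns. SAP 3.3.1 nevertheless names 50% as its CT target. A larger effect also lowers the event count: at CT 22% with a 65% reduction, 200.7 × 0.22 × 1.35 = 59.6 women, below 66 although Table 2 gives 96% power. The plan should say what happens then.

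**Repeat infections add power.** Protocol section 10 expects this and the planned GEE analysis would use them. They cannot help a floor counted in women, and the gain is not quantified in the plan.

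**CT alone is a secondary endpoint (SAP 2.2.2).** Agreed, and this limits the weight of the point. A reader might also infer that a null CT result on fewer than 66 women could never be called definitive. That is a preference about interpretation, not something the documents establish.

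**Conclusion.** The point holds as an inconsistency and a missing rule that should be fixed. At N=446, with 22% taken as the any-STI rate, both the 66-woman CT floor and 80% first-event power for a 50% CT reduction need a CT share of about 99%. At N=550 they need about 80%, so the Protocol summary's CT power claim is not refuted at that size, but it rests on an unstated share and sits beside two different sample sizes.

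The size of any shortfall depends on that share. At assumed shares of 82% and 68%, about 54 and 45 women with CT are expected at N=446, with power of 71% and 63% for a 50% reduction and 92% and 87% for a 65% reduction. These figures assume 10% loss, first events only and the SAP's proportions. If control-arm CT is 22% or more, there is no expected shortfall at a 50% effect, and the error is then the any-STI label. Either way, the re-estimation clause does not respond to CT. Power for the primary endpoint is unaffected.

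**What to change.** 1. **SAP 3.3.1: state the CT assumption.** Either label 22% as the CT rate and give the any-STI rate separately, or keep 22% for any STI and say that first-event CT power at N=446 is below 80% for a 50% reduction. In the second case cite Table 2 for both effect sizes at CT 18% and 15% (71% and 63%; 92% and 87%), and mark the CT share as an assumption. In the Protocol summary, tie the CT power claim to one sample size.
2. **SAP 3.3.2: add the observed CT rate** to the condition for action, using the levers already listed there (additional enrollments or person-time).
3. **SAP 4.2: make the timing of the final analysis consistent with the 66-CT floor**, including what is done if the floor has not been reached at the last 12-month visit.

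The cost is wording. The one downside is a less favourable CT power figure if 22% is kept for any STI. Women or person-time would be added only if the team acts to meet the floor it has already set.

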**Table 2 Power Table for N = 446; 1:1 randomization dPEP: SOC**

Control arm incidence	Power to detect 50% reduction (Number of infections for 80% power = 66)		Power to detect 65% reduction (Number of infections for 80% power = 52)	
	Intervention arm incidence	Power	Intervention arm incidence	Power
50%	25.0%	99%	17.5%	99%
33%	15.5%	93%	11.6%	99%
22%	11.0%	80%	7.7%	96%
18%	9.0%	71%	6.3%	92%
15%	7.5%	63%	5.2%	87%

### **3.3.2. Sample Size Re-estimation**

At the point when enrollment is near completion, the study team will evaluate the expected power of the trial, based on the observed rate of infections. If the rate of the primary endpoint is substantially lower than anticipated, sample size re-estimation would be used to restore power to the extent possible, through additional enrollments, increase in person-time, or modification of risk criteria.

